Remote Ischemic Conditioning (RIC) in Recipients of Brain Death Donor Livers –

A Feasibility and Safety Study

NCT02635347

October 1 2017

RIC Liver Recipients – Data Analysis Plan

RIC Liver Recipients – Data Analysis Plan

Available Data

- RECIPIENT Baseline Characteristics
 - Study Group
 - Hospital Days (#)
 - Post-Transplant Hospital Days (#)
 - Age, years
 - Gender
 - Ethnicity
 - American Indian/Alaska Native
 - Asian
 - Native Hawaiian
 - African American
 - Hispanic/Latino
 - White
 - More than 1 race
 - Unknown/not reported
 - Height
 - Weight
 - BMI
 - Beta blockers at transplant (y/n)
 - CCB at transplant (y/n)
 - Primary Etiology, Secondary etiology
 - EtOH
 - HBV
 - HCV
 - Cryptogenic/NAFLD
 - AIH
 - PBC
 - PSC
 - Budd-Chiari
 - Wilson's
 - Alpha-1 Antitrypsin
 - Biliary atresia
 - Other
 - HCC (y/n) – based on path report
 - HTN
 - CAD
 - Hx of MI
 - Peripheral vascular disease

- Peripheral neuropathy
- HIV
- Asthma
- COPD
- PNA
- Current smoker
- DM
- CKD
- On dialysis at time of Tx
- Serum creatinine
- eGFR
- Total Bilirubin
- INR
- MELD
- Pressors (y/n)
- Hypertonic saline (y/n)
- Mechanical ventilation (y/n)
- Days of mechanical ventilation
- Donor Baseline Characteristics
 - Age, years
 - Gender
 - Race
 - White
 - African American
 - Hispanic/Latino
 - Asian
 - Native American
 - Other
 - Height
 - Weight
 - BMI
 - Cause of death
 - Hospital days
 - OPO
 - Local
 - Regional
 - National
 - Donor receiving glucocorticoids
 - Donor on sulfonylureas
 - Pre-recovery biopsy performed
 - Macrosteatosis
 - Microsteatosis

- DRI
- Operative Variables
 - Anesthesia Maintenance agent (each y/n)
 - Sevo
 - Iso
 - Des
 - Other
 - Propofol used for induction (y/n)
 - Surgery length (min)
 - CIT (min)
 - WIT (min)
 - Veno-venous bypass used (y/n)
 - Piggypack or bicaval
 - Crystalloid (liters)
 - Albumin (liters)
 - RBC (units)
 - FFP (units)
 - Platelets (units)
 - Cryo (units)
 - Other fluid (likely nothing in this field)
 - UOP (liters)
 - EBL (liters)
 - Post-implantation biopsy (y/n)
 - Fields exist for %macro and %microsteatosis but these are all empty because the slides have not been reviewed.
- POST-Operative Variables
 - Propofol for sedation POST-OP (y/n)
 - ICU LOS (days)
 - POD 0-7 (8 values total)
 - AST
 - ALT
 - Total Bilirubin
 - INR
 - Creatinine (if not on HD to begin with and if not already in stage III AKI pretransplant)
 - Time to extubation
 - Reintubated within 7 days (y/n)
 - Early allograft dysfunction – EAD (y/n)

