 - Prolonged respiratory insufficiency – PRI (y/n)
 - Stage 2 AKI (y/n)
 - Stage 3 AKI (y/n)
 - Pre- and post-transplant dialysis and whether or not it was discontinued in the hospital

- Time to dialysis discontinuation
- Clavien Dindo – all for 30 day complications
 - 3b (y/n)
 - 4a (y/n)
 - 4b (y/n)
 - 5, ie. Death (y/n)
 - Highest complication grade
 - Any complication greater than or equal to 3b (y/n)
 - Number of 3b or higher complications
- Survival PATIENT – 90 days
 - (y/n) and number of days
- Survival GRAFT – 90 days
 - (y/n) and number of days
- Dialysis – 90 days
- Creatinine at 90 days if not on dialysis
- eGFR at 90 days
- Completed study (y/n)

Statistical Analysis Plan

No comparison (one group)

- All feasibility data
 - Proportion of all patients who tolerated all 6 interventions
 - Proportion of patients who were intubated for all 6 interventions
 - Proportion of patients who were extubated for at least one intervention and tolerated all 6 interventions
 - For extubated patients: number of interventions tolerated while extubated. Break down into those who tolerated all 6 vs those who didn't tolerate all 6.
 - Mean/median pain score for patients receiving an intervention
 - Present as mean/median plus/minus STDEV/IQR for pain scores and number of interventions. Also histograms would be useful for these as the pain scores are likely going to end up being bimodally distributed.
 - Present as proportions with confidence intervals for all others.

Bivariate analyses – categorical data

Chi-squared or Fisher's exact tests.

- Recipient baseline characteristics
 - Gender, beta blockers at transplant (y/n), CCB at transplant (y/n), HCC (y/n) – based on path report, HTN, CAD, Hx of MI, Peripheral vascular disease, Peripheral neuropathy, HIV, Asthma, COPD, PNA, Current smoker, DM, CKD, On dialysis at time of Tx, Pressors (y/n), Hypertonic saline (y/n), Mechanical ventilation (y/n)
- Donor baseline characteristics
 - Gender, Donor receiving glucocorticoids, Donor on sulfonylureas, Pre-recovery biopsy performed (y/n)
- Operative Variables
 - Propofol used for induction (y/n), Veno-venous bypass used (y/n), Piggypack or bicaval, Post-implantation biopsy (y/n)
- POST-operative Variables
 - Propofol for sedation POST-OP (y/n), Reintubated within 7 days (y/n), **Early allograft dysfunction – EAD (y/n), Prolonged respiratory insufficiency – PRI (y/n)**, Pre- and post-transplant dialysis and whether or not it was discontinued in the hospital

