 - Stage 2 AKI (y/n)
 - Stage 3 AKI (y/n)
 - These need to be discussed. The ideal method for comparison would be as an ordinal variable, using a CMH test. However, numbers may end up being low. Alternatively, can analyze as one y/n (ie. Stage 2 or 3 AKI) or using exact chi-squared.
- Clavien Dindo – all for 30 day complications

- 3b (y/n), 4a (y/n), 4b (y/n), 5 ie. Death (y/n)
 - These need to be discussed. We can analyze each individual complication grade using a 2x2 table. Analysis using an ordinal scale doesn't make sense, unless we take only the highest grade, for example.
 - Death also needs to be discussed. Later, we have 90 day mortality data (yes/no) as well as data regarding number of days survived. So we need to decide (a) if we are including death here at all, (b) if we end up analyzing 2x2 tables, is there any point to analyzing 30 day death separately from 90 days, I think no.
- Any complication greater than or equal to 3b (y/n)
- Other data
 - 90 day patient survival (y/n)
 - Can also analyze using Kaplan-Meier estimates
 - Should we consider gathering the data past 90 days? Our protocol does not say we would do this.
 - 90 day graft survival (y/n)
 - Can also analyze using Kaplan-Meier estimates
 - Patient on dialysis at 90 days (y/n)

Chi-squared or Exact Chi-squared tests (categorical variables with more than two levels for the outcome).

- Recipient baseline characteristics
 - Ethnicity, Primary/secondary etiology of cirrhosis,
- Donor baseline characteristics
 - Ethnicity, OPO (local/regional/national), Cause of Death,
- Operative variables
 - Anesthesia type
- POST-operative variables
 - Stage 2 / Stage 3 AKI (see discussion above)
- Clavien-Dindo
 - Complication grades (see discussion above)

Cochran–Mantel–Haenszel test for Ordinal Data

- Stage 2/3 AKI, Complication grades (see discussion above)

Bivariate analyses – Continuous Data

Student's T-Test vs Mann-Whitney U test

- Recipient baseline characteristics

- Hospital Days (#), Post-Transplant Hospital Days (#), Age years, Height, Weight, BMI, Serum creatinine, eGFR, Total Bilirubin, INR, MELD, Days of mechanical ventilation
- Donor baseline characteristics
 - Age years, Height, Weight, BMI, Hospital days, Macrosteatosis, Microsteatosis, DRI
- Operative variables
 - Surgery length (min), CIT (min), WIT (min), Crystalloid (liters), Albumin (liters), RBC (units), FFP (units), Platelets (units), Cryo (units), Other fluid (likely nothing in this field), UOP (liters), EBL (liters)

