 - Macro/microsteatosis if data become available
- POST-op variables
 - ICU LOS (days)
 - POD 0-7 (8 values total)
 - AST, ALT, Total Bilirubin, INR, Creatinine (if not on HD to begin with and if not already in stage III AKI pretransplant)
 - Here, we need to decide how the data will be analyzed. There are three options: day-by-day comparisons, an omnibus test such as a factorial ANOVA (there will be a problem with missing data if we do this), and bivariate longitudinal linear regression (my personal preference, this accounts for correlation between observations within a subject on different days but at the same time uses all the data)
 - Time to extubation
 - Time to dialysis discontinuation
- Clavien-Dindo
 - Number of 3b or higher complications
- Creatinine at 90 days, eGFR at 90 days.

Multivariate regression analysis

- Logistic regression
 - EAD, PRI, Stage 2/3 AKI
- Longitudinal linear regression
 - AST, ALT, Total bilirubin, INR, Creatinine

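### Time to dialysis discontinuation is tested only in patients who were dialysed and stopped, a subset that RIC may itself change, so the comparison can mislead in either direction

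*SAP*

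**What the plan says.** The SAP names "Time to dialysis discontinuation" under POST-Operative Variables in the Available Data list, and again under POST-op variables in Bivariate analyses – Continuous Data. The test heading for that section is "Student's T-Test vs Mann-Whitney U test".

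No analysis population is given for the variable, no value is assigned to a patient who was never dialysed, and no rule covers a patient who dies on dialysis or is still on it. The data list also includes "Pre- and post-transplant dialysis and whether or not it was discontinued in the hospital", so dialysis that starts after transplant is within scope. Baseline status is recorded ("On dialysis at time of Tx") but is not used to define or stratify this comparison.

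Other items are treated differently:
- The laboratory series has a restriction on pre-transplant status: "Creatinine (if not on HD to begin with and if not already in stage III AKI pretransplant").
- "Patient on dialysis at 90 days (y/n") has an answer for patients who were never dialysed.
- "Can also analyze using Kaplan-Meier estimates" is written under 90-day patient and graft survival, not here.
- The logistic models cover "EAD, PRI, Stage 2/3 AKI"; no model covers dialysis duration.

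**The concern.** For a recipient who was not on dialysis at transplant, needing dialysis is an outcome. A test of how long dialysis lasted then compares two groups of patients picked out by that outcome. If RIC changes who needs dialysis, the picked groups differ in severity even if the full groups were alike at transplant. Complete follow-up does not cure this: the problem remains if every patient survives and every patient stops.

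The bias has no fixed sign. If RIC mainly prevents short courses, the RIC patients still dialysed are the sicker ones, and RIC looks slower to recover. If RIC prevents long courses, or adds short ones, it looks faster although no individual course was shortened. At stake is a reported duration difference that readers would take as an effect on renal recovery.

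**Working it through.** **No figure to reproduce.** The SAP gives no sample size, dialysis rate or dialysis duration. Every rate and duration below is an assumption, chosen to show the mechanism.

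**Formulas.** With rate p and mean duration d for each type of course:
- mean among the dialysed = Σ(p × d) / Σp
- dialysis days per 100 patients = 100 × Σ(p × d)

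**Main illustration.** Nobody is on dialysis before transplant. In each arm 10% need long dialysis (mean 30 days). Short dialysis (mean 5 days) is needed by 20% of controls and 10% of RIC patients.
- Control: (0.10×30 + 0.20×5)/0.30 = 4.0/0.30 = 13.3 days; 400 days per 100 patients.
- RIC: (0.10×30 + 0.10×5)/0.20 = 3.5/0.20 = 17.5 days; 350 days per 100 patients.
- RIC looks 4.2 days slower (17.5/13.3, about 31% longer) while total dialysis falls by 50 days per 100 patients.

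**The opposite direction, same inputs.**
- RIC adds short courses (10% to 20%): 17.5 days in control, 13.3 in RIC. RIC looks faster while total dialysis rises from 350 to 400 days per 100.
- RIC halves the long courses (10% to 5%) and leaves short ones at 20%: (0.05×30 + 0.20×5)/0.25 = 10.0 days against 13.3. RIC looks faster to recover although no course became shorter.

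**Other inputs.** With 10% mild (5 days) and 10% severe (20 days) in control, and half the mild cases prevented, the means among the dialysed are 12.5 (control) and 15.0 days (RIC). Counting zero for the never dialysed, they are 2.50 and 2.25 days. The sign again reverses.

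**What weakens the effect.**
- Pre-transplant dialysis: adding 20% per arm (mean 10 days) to the main illustration gives (4.0 + 2.0)/0.50 = 12.0 against (3.5 + 2.0)/0.40 = 13.75 days, so the gap falls from 4.2 to 1.75 days. With 10% mild (5 days), 10% severe (10 days) and 20% pre-transplant (3 days), the gap is only 0.02 to 0.08 days.
- A true shortening of long courses: in the main illustration, cutting RIC's long mean from 30 to 21 days gives (0.10×21 + 0.10×5)/0.20 = 13.0 days against 13.3, so the bias is about cancelled.

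**Simulation of the main illustration** (exponential durations, arm sizes assumed). RIC shows the longer mean among the dialysed in about 64% of trials at 40 per arm and 73% at 100 per arm, against 50% with no effect. At 40 per arm the comparison rests on about 12 control and 8 RIC patients. A Mann-Whitney result at p<0.05 in the RIC-slower direction occurs in about 6% of those trials, against about 2.5% with no effect.

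**The case against.** **The restriction is inferred.** The SAP nowhere says that only dialysed patients are analysed, and a protocol not at hand may define the variable more closely. But a never-dialysed patient has no time to discontinuation, and the named tests can use only values that exist. The inference is safe for the test as written. How many new starters would enter the set is unknown.

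**The illustration is a favourable case.** It omits pre-transplant dialysis and assumes that RIC leaves long courses untouched. Relaxing either shrinks or cancels the bias, as shown above. This stands, and it limits the claim to a possible bias of unknown size and sign.

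**The consequence is small.** This is one of many bivariate comparisons in a feasibility and safety study, and it is in no regression model. Dialysis status, AKI stage and dialysis at 90 days are compared separately, so fewer dialysed RIC patients would be visible. This too stands. However, nothing in the SAP tells the reader to interpret duration alongside those items.

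**Stronger readings that the SAP does not support.**
- A reader might infer that RIC will look slower. That follows only if the prevented courses are shorter than average and the remaining ones are unchanged.
- A reader might extend the point to the categorical item on whether dialysis was discontinued in hospital. That item can be read as a table of all patients (never dialysed, stopped, not stopped), and the SAP does not restrict it to the dialysed.
- A reader might infer that the planned test is sound in recipients already on dialysis at transplant. Membership of that group is fixed at baseline, but a value still exists only for those who stopped, so the tested set remains selected by outcome unless death and continuing dialysis are handled.

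**Conclusion.** The point holds as a cheap improvement to a secondary variable. As written, the between-group test of dialysis duration compares subsets selected partly by a post-transplant outcome, and no other provision of the SAP corrects this. Under the main assumptions, an apparent delay of 4.2 days accompanies a true saving of 50 dialysis days per 100 patients; under other plausible inputs the distortion is near zero or runs the other way. The illustration rests on assumed rates and durations, no pre-transplant dialysis and no change in long courses. At the small arm sizes considered, the main harm is a misleading estimate: a significant result in the wrong direction is uncommon.

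**What to change.** Split the variable by dialysis status at transplant, which is already recorded.

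1. **New starters:** report time to discontinuation as description only, with no between-group test.
2. **All recipients not on dialysis at transplant:** compare new post-transplant dialysis (y/n), and days alive and off dialysis to day 90 by Mann-Whitney, with each day dead or on dialysis counting zero.
3. **All recipients on dialysis at transplant:** analyse time to discontinuation as time-to-event, with continuing dialysis censored at day 90 and death as a competing event.

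**Cost.** SAP wording, plus a chart look-up of dialysis start and any restart dates for the few new starters, since the SAP lists neither. The all-patient measure has limits to state openly. It combines death with dialysis, and many values will be tied: in the main illustration 70% of controls and 80% of RIC patients are never dialysed. There, with no deaths, its Mann-Whitney test detects the assumed benefit in only about 14% of trials at 40 per arm. The gain is a comparison of like with like; power stays low.

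### The SAP compares 90-day creatinine and eGFR without adjustment, although the pre-transplant values are recorded; adjusting for them would gain some precision at almost no cost

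*SAP*

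**What the plan says.** The last line of the SAP section *Bivariate analyses – Continuous Data* names "Creatinine at 90 days, eGFR at 90 days". The only method given for that section as a whole is "Student's T-Test vs Mann-Whitney U test", and neither test takes a covariate.

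The same section lists the recipients' pre-transplant measurements, among them "Serum creatinine, eGFR, Total Bilirubin, INR, MELD". The categorical section lists "CKD, On dialysis at time of Tx" among the recipient characteristics. The stated use of all of these is a between-group test of baseline.

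The section *Multivariate regression analysis* has two parts. Logistic regression covers "EAD, PRI, Stage 2/3 AKI". Longitudinal linear regression covers five laboratory values, the same five that the continuous section lists for postoperative days 0 to 7: "AST, ALT, Total Bilirubin, INR, Creatinine". The multivariate section does not list eGFR, a 90-day value or any covariate.

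The SAP does restrict by starting kidney function in the early postoperative series: "Creatinine (if not on HD to begin with and if not already in stage III AKI pretransplant". At 90 days the written condition concerns current dialysis only, and only for creatinine: "Creatinine at 90 days if not on dialysis".

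**The concern.** A patient's creatinine or eGFR 90 days after transplant is likely to depend in part on kidney function before it. When the baseline value is at hand and left out of the comparison, two things follow. The part of the between-patient spread that baseline could explain stays in the standard error. Any difference between the groups in starting kidney function also passes, in proportion, into the 90-day difference. Testing baseline for imbalance, as the SAP does, corrects neither.

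At stake is how well two secondary outcomes can be read. If the model is not fixed in advance, there is also room to decide on adjustment after seeing which baseline tests came out significant.

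**Working it through.** **Inputs from the SAP.** The documents supply the test assignments and the list of recorded baseline fields. They give no sample size, SD, correlation or effect size, so there is no figure of the plan's own to reproduce. Everything numerical below is illustration under assumptions.

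**Is there an adjusted analysis of the 90-day values?**
- eGFR at 90 days: t-test or Mann-Whitney only. eGFR is absent from the multivariate section.
- Creatinine at 90 days: t-test or Mann-Whitney. Creatinine does appear under longitudinal regression, but as one of the same five laboratory values as the day 0 to 7 series, with no 90-day time point and no covariates. That it refers to the early series is an inference, though a natural one.

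**Precision.** Let *r* be the correlation between the pre-transplant and 90-day value. In large samples, adjustment multiplies the standard error by √(1 − r²).

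| r | variance removed (r²) | SE ratio √(1 − r²) | fall in SE |
|---|---|---|---|
| 0.3 | 0.09 | 0.954 | 5% |
| 0.5 | 0.25 | 0.866 | 13% |
| 0.6 | 0.36 | 0.800 | 20% |

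In small samples, estimating the slope costs a little. For one normally distributed covariate and N patients in total, the expected variance is multiplied by 1 + 1/(N − 4). With an assumed 20 per arm (N = 40) this is 1 + 1/36 = 1.028. The SE ratio becomes √(0.91 × 1.028) = 0.967 at r = 0.3 and √(0.64 × 1.028) = 0.811 at r = 0.6, so the falls are about 3% and 19%.

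**Power, for scale.** Assume 20 per arm, a true effect of 0.5 SD and two-sided alpha 0.05 (normal approximation).
- SE = √(2/20) = 0.316 SD, and 0.5/0.316 = 1.58. Unadjusted power is Φ(1.58 − 1.96) = 0.35.
- Dividing 1.58 by the large-sample SE ratio gives 0.38 at r = 0.3 and 0.45 at r = 0.5.

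**Chance imbalance.** With equal SDs at both times, a baseline difference of *d* SD moves the unadjusted 90-day difference by r × d. For d = 0.5 this is 0.15 SD at r = 0.3 and 0.25 SD at r = 0.5. Under randomisation, the chance of a baseline difference of at least 0.5 SD in either direction is 2[1 − Φ(0.5/√(2/n))]:
- 10 per arm: 26%
- 20 per arm: 11%
- 40 per arm: 2.5%

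At 20 per arm, given that an imbalance of 0.5 SD has occurred, the false-positive rate of the unadjusted test is 0.065 at r = 0.3 and 0.089 at r = 0.5. Averaged over all possible imbalances it stays at 0.05.

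**The case against.** The strongest reply is that an unadjusted two-group test is not an error. Under random allocation it is unbiased and keeps its type I error, because its standard error already includes the spread due to baseline. Assume an SD of 25 mL/min at both times and 50 per arm. The standard error is then 25 × √(2/50) = 5 mL/min, and a baseline imbalance of one standard error with a slope of 0.3 to 0.7 shifts the result by 1.5 to 3.5 mL/min, or 0.3 to 0.7 of a standard error. That lies within the uncertainty already reported. This stands: a reader might infer that the planned comparison is biased, and the SAP does not support that. Only if groups were not randomised would confounding arise, and the SAP is silent on assignment.

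A reader might also infer from the recorded fields that recipients differ widely in starting kidney function. The SAP lists variable names and reports no data, so neither a wide spread nor an imbalance is shown.

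It is fair, too, that these are secondary outcomes in a feasibility and safety study, and that the correlation may be weak. The SAP foresees dialysis and stage III AKI before transplant, so some baseline values may predict day 90 poorly. Finally, the multivariate section names no covariates for any outcome, which is the broader gap.

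None of this favours the unadjusted test over the adjusted one. The baseline data are already collected, and the plan itself uses regression for other outcomes and restricts early creatinine by pre-transplant kidney status.

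**Conclusion.** The point holds as a low-cost improvement to a stated method, not as a fault that invalidates an analysis. The 90-day values of creatinine and eGFR have no stated adjusted analysis, while the covariate that matters most is on file.

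With randomisation, the loss is precision and exposure to chance imbalance; without it, confounding is added. The gain cannot be sized from the SAP. It is about 5% to 20% of the standard error for an assumed correlation of 0.3 to 0.6, slightly less in small arms, and close to nothing if the correlation is weak. No feasibility result depends on it.

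Baseline adjustment should not be read as making the 90-day kidney comparison clean. Creatinine is measured only in survivors who are not on dialysis at that time, and that selection after transplant remains.

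**What to change.** Add to the SAP, for these two secondary outcomes:

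- **Main comparison:** linear regression of 90-day eGFR, and of log 90-day creatinine, on study group and the pre-transplant value of the same measure (log creatinine for creatinine). Include patients not on dialysis at transplant, in line with the SAP's own restriction for day 0 to 7 creatinine. Report the adjusted difference with its confidence interval.
- **Sensitivity analysis:** the same model in all patients with a 90-day value, adding an indicator for dialysis at transplant.
- **Support:** keep the planned t-test or Mann-Whitney test.
- **Limit to state:** adjustment does not remove the selection from measuring creatinine only in survivors not on dialysis at 90 days. Present the results beside the numbers who died and who were on dialysis by 90 days in each group.

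The cost is a few sentences and one or two model degrees of freedom, with no new data. The main analysis leaves out patients dialysed at transplant, so the population it describes must be named.

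### The logistic models for EAD, PRI and Stage 2/3 AKI have an open covariate set and no sparse-data method; with few events the adjusted odds ratio may be inestimable, imprecise or biased

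*SAP*

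**What the plan says.** Under the heading "Multivariate regression analysis", the logistic regression entry in the SAP consists of the outcome list "EAD, PRI, Stage 2/3 AKI". It names no covariates, selection rule, limit tied to the number of events, estimator, or procedure if a fit separates.

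The bivariate sections treat the same outcomes with more care. EAD and PRI fall under "Chi-squared or Fisher's exact tests". For Stage 2 and Stage 3 AKI the SAP calls an ordinal CMH test ideal, then adds "However, numbers may end up being low" and offers a fallback: "Alternatively, can analyze as one y/n (ie. Stage 2 or 3 AKI) or using exact chi-squared". It marks that choice as still to be discussed.

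The document describes the trial as "A Feasibility and Safety Study". It states no sample size, event rate or expected effect; these may be in the protocol, and their absence is not part of this point.

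**The concern.** A regression with several covariates asks more of the data than a 2×2 table. The SAP protects the 2×2 table against small counts but not the regression on the same outcomes.

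The covariate set is also wide open. The bivariate sections list about 49 recipient and donor variables, or about 66 with the operative ones. The recipient baseline list even contains the number of hospital days after transplant, which is not a baseline measure. Nothing in the plan keeps such a variable out of a model.

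The adjusted RIC odds ratios are at stake. EAD and PRI are the outcomes set in bold in the SAP, so their results are likely to be read closely. With few events per term the model may give no estimate, a very wide interval, or an estimate too far from 1. The SAP's notes on which data fields are still empty suggest that data were already in hand, so covariates left open could be chosen after results are seen.

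**Working it through.** **Inputs.** The SAP has no figure to reproduce. From it come only the outcomes, the lack of a covariate list and the warning about AKI numbers. Everything numerical below is assumed: 1:1 allocation; N = 40, 80, 100 or 200; control event rate 10%, 25% or 40%; 2, 5 or 10 independent normal covariates, each with log odds ratio 0.3; true adjusted RIC odds ratio 0.5.

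**Method.** 1,000 trials were simulated per setting, and each was fitted by ordinary maximum likelihood (ML) and by Firth penalised likelihood.

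- Events per variable: EPV = mean events / (covariates + 1).
- Relative bias = mean estimated log-OR / ln(0.5) − 1, among fits that converged; ln(0.5) = −0.693.
- Odds ratios are geometric means.

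Example for N = 40, 25%, five covariates: EPV = 8.10 / 6 = 1.35. The ML odds ratio is 0.39, so ln(0.39) / ln(0.5) = 0.942 / 0.693 = 1.36, an excess of about 36% from the rounded value and 35% unrounded.

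| N | Control rate | Covariates | Events | EPV | ML fits failed | ML OR | ML bias, log-OR | Firth OR |
|---|---|---|---|---|---|---|---|---|
| 40 | 10% | 2 | 2.95 | 0.98 | 42% | 0.70 | −49% | 0.59 |
| 40 | 10% | 10 | 3.13 | 0.28 | 90% | 0.41 | +30% | 0.70 |
| 40 | 25% | 2 | 7.97 | 2.66 | 5% | 0.48 | +7% | 0.51 |
| 40 | 25% | 5 | 8.10 | 1.35 | 6% | 0.39 | +35% | 0.50 |
| 40 | 25% | 10 | 8.29 | 0.75 | 37% | 0.26 | +92% | 0.51 |
| 80 | 10% | 2 | 6.04 | 2.01 | 13% | 0.57 | −18% | 0.54 |
| 80 | 25% | 5 | 16.02 | 2.67 | 0% | 0.44 | +18% | 0.50 |
| 100 | 25% | 2 | 19.69 | 6.56 | 0% | 0.46 | +12% | 0.48 |
| 100 | 40% | 2 | 32.85 | 10.95 | 0% | 0.49 | +2% | 0.51 |
| 200 | 25% | 5 | 40.16 | 6.69 | 0% | 0.48 | +7% | 0.49 |

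**Reading the results.**

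1. With about 8 or more events and EPV below 3, ML is biased away from 1, from +2% to +95% over all settings run. The bias grows as covariates are added.
2. At EPV of 6 or more, the ML bias is between +2% and +12%. Part of the +12% is simulation noise, since Firth also shows +5% in that setting.
3. With about 3 events, 42% to 90% of ML fits fail. With about 6 events, 13% to 31% fail. The fits that survive can lie on either side of the truth.
4. With a true odds ratio of 1, the three settings run give ML odds ratios of 0.99 to 1.02, so there is no systematic bias.
5. Firth gives 0.47 to 0.54 wherever there are about 6 or more events. With about 3 events it shrinks toward the null, to 0.59 to 0.70.

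**Precision.** A separate simulation used 2,000 trials per setting, about 25% events and six covariates, two of them prognostic with log odds ratios 0.6 and 0.4 per SD. Root mean squared error of the log-OR, ML against Firth, was 1.40 against 0.88 at N = 40, 0.93 against 0.69 at N = 60, and 0.58 against 0.51 at N = 100. Mean ML log-OR at N = 40 was −0.993, so squared bias is (0.30 / 1.40)² ≈ 5% of the mean squared error. Imprecision is the larger part of the problem.

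**The case against.** A reader might infer that the plan expects low numbers for all three outcomes and that the adjusted odds ratios will therefore be exaggerated. The SAP does not support that.

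- The warning says only that numbers may be low, and it concerns AKI. Nothing of the kind is said of EAD or PRI.
- Maximum likelihood is not named. It is the usual default when a plan says logistic regression, but that is an inference.
- Without a sample size, event rate or covariate count, no bias can be demonstrated. It is small if events are plentiful, absent if RIC has no effect, and can run toward the null if events are very few.
- The SAP does not say that covariates will be chosen by bivariate p-values or after results are seen. It only leaves this open.
- The AKI fallback to a single yes/no outcome can be read as what the logistic model uses, so the AKI entries need not conflict.
- This is a feasibility and safety study, and the SAP attaches no success criterion to these models. Firth is one defensible choice; exact logistic regression is another.

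All of this stands, and it limits the point to a conditional one. It does not remove it: the regression lacks the small-sample provision that the simpler comparisons of the same outcomes have, and an unlimited covariate count is what drives events per variable down.

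**Conclusion.** The point holds as a conditional weakness and a cheap improvement, not as a demonstrated bias. The logistic models for EAD, PRI and Stage 2/3 AKI have no covariate limit and no sparse-data method. If events per variable turn out to be few, default maximum likelihood may fail, be very imprecise, or overstate a non-null RIC effect.

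The illustrative sizes of +35%, +18% and +7% on the log odds ratio (N = 40, 80 and 200, five covariates) rest wholly on the assumed 25% control rate, odds ratio of 0.5, 1:1 allocation and covariate effects. Firth removes most of the bias when events are sparse and nearly matches maximum likelihood when they are not (0.49 against 0.48 at N = 200), so little is lost by naming it in advance.

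**What to change.** Amend the logistic regression entry as follows.

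- Fit each model by Firth penalised likelihood, with profile-penalised 95% confidence intervals.
- Include study group and a short list of pre-transplant prognostic variables from the SAP's own lists, for example MELD and DRI. Fix the list and its order of priority before any group comparison is examined.
- Cap the number of covariates by the total number of events in both groups combined, and write the rule as a number.
- Do not select covariates by bivariate p-values, and exclude anything measured after transplant.
- Label the models exploratory.
- State an event count below which no adjusted model is fitted and only the exact unadjusted comparison is reported. The calculations show Firth unreliable at about 3 events and acceptable at about 6, so the threshold belongs in that region.

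The cost is a few lines of SAP text and a standard software option. The downside is that imbalance in other covariates is left unadjusted. Firth does not rescue extremely sparse data, which is why the last rule is needed.
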